2.3 Report Generation

The final statistical reports will describe and justify any deviations from the original statistical plan described herein. Analyses will be performed using SAS 9.4 software and most current version of R. No adjustments for multiple comparisons will be made. All programs used to produce this report will be documented, tested, and archived and all tables, figures and listings will be validated before considered final.

2.4 Definition of the Analysis Populations

Enrollment and screening summaries will be generated using all screened participants. All participant disposition, secondary, exploratory, and safety summaries will be performed using an intent to treat (ITT) population, defined as all participants randomized at Visit 1 (Day 0). The primary analyses in both Study A and Study B will be performed using a per-protocol analysis (PPA) population, as defined below. Sensitivity analyses, repeating the primary analyses, will be done on the ITT population. Secondary analyses will likewise be run on the PPA population and repeated on the ITT population.

PPA is defined by the following criteria:

1. Daily diary completion ("Compliance") from Week 0 (Visit 1) to Week 6 (Visit 3)
 - a. $\geq 70\%$ non-missing data
 - b. $\geq 70\%$ non-missing in last 2 weeks

2. Daily diary responses from Week 0 (Visit 1) to Week 6 (Visit 3) aligned with randomized treatment (“Adherence”)
 - a. to assigned treatment regimen (HS or Dnase) among non-missing days overall (>=70%)
 - b. to assigned treatment regimen (HS or Dnase) among non-missing days in 2 weeks (>=70%)
3. No initiation of new acute oral, inhaled, or IV antibiotics for respiratory symptoms (rate from ETI trial was ~5%) from Week 0 (Visit 1) to Week 6 (Visit 3)
4. Non-missing FEV at Week 6 (Visit 3)
5. Given the correct randomization instructions
6. Minimum 70% use of ETI among non-missing days in last 2 weeks
7. Eligible at Week -2 (Screening Visit) and at Week 0 (Visit 1, Randomization)

Data from subject disposition visits will be allocated to the nearest subsequently scheduled visit. Missing outcome data in the ITT population for the final primary analysis and for key secondary analyses (CRISS, CFQ-R, and LCI) will be imputed using the least favorable treatment mean in arms discontinuing treatment and using the most favorable treatment mean in arms continuing treatment. Complete case results, including participants based on availability of non-missing values, will also be reported.

3. Overview of Planned Analyses

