14.2 Analysis of Primary Endpoint

The primary hypothesis for both Study A and Study B is that discontinuing therapy is non-inferior to continuing therapy, as measured by the 6-week change in FEV₁ % predicted. The primary endpoint for each study is the difference between arms in the change in FEV₁ % predicted from randomization to

week 6. The primary analysis for non-inferiority will be conducted on the PPA population. A linear model will be used to adjust for randomization strata as specified in Section 8.1. The estimated effects of discontinuation and corresponding 95% confidence intervals will be reported for both studies A and B, and p-values will be evaluated for a one-sided alpha-level 0.025 test of non-inferiority with a margin of -3% absolute change in FEV₁ % predicted for each study.

The lower lung function cohort, if enrolled, will not be included in the primary analysis, but will be analyzed as a separate cohort for which the primary and secondary analysis within this cohort will focus on the evaluation of safety. Further details will be provided in the SAP.

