The following table summarizes changes from the original, approved statistical analysis plan and/or study protocol. A brief description of the change, addition or deletion is provided as well as the rationale for each change and date the change was identified. Minor wording or formatting changes or inclusion of clarifying language or footnotes are not included in this table.

Section or Exhibit Number	Description of Change	Rationale for Change	Date of Change
Section 1.2 DMC Interim Analysis	Included 12% loss of follow-up to enrollment projections for DMC interim reports	Clarification	9/2021
Section 2.4: Analysis Populations	Added #7 to PPA definition: excluding enrolled but ineligible participants	Some participants were determined to be ineligible after enrollment constituting a protocol violation – this was unexpected and therefore not prespecified	3/2021
Section 2.4: Analysis Populations	Extended the missing data imputation method used for the primary endpoint for use in key secondary endpoints (CRISS, CFQ-R and LCI)	Aligns with sensitivity analysis for the primary endpoint	3/2021
Section 3.2.4 Adverse Event results and Table 4.10	Proportion of participants with temporary or permanent therapy modifications was a prespecified safety endpoint in the protocol. Here it is described specifically as therapy modifications occurring due to an adverse event.	Clarification	3/2021
Section 3.2.7 Spirometry results, Table 7.2 and Figure 7.3	The subgroup analyses for the primary endpoint are further specified.	The primary endpoint repeated among subgroups was an originally specified analysis, but the specific subgroups were not defined in the original SAP. The specific subgroups were pre-specified in the SIMPLIFY study design paper [1].	1/2021
Section 3.2.13 Lower Lung Function (LLF) Cohort	Added descriptions of analysis to be performed among the LLF cohort for the interim and final analysis	Enrollment in the LLF cohort was contingent on DMC approval after review of safety data. A subset of the analyses specified in the SAP were identified for inclusion in a LLF specific report.	9/2021
Table E.3.2, 2.1 Summary of Baseline Characteristics	Added baseline indicator of chronic systemic steroid use	Oversight	3/2021
Table 3.1 Summary of Withdrawals	Increased maximum withdrawal date (loss to follow-up) from 49 to 60 days	A loss to follow-up of 60 days aligned better with the study follow-up period and allowed ample time for research coordinator contact effort	3/2021

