3.2.6. Analyses of Primary Endpoint

The primary endpoint is the difference between arms in the change in FEV₁ % predicted from Week 0 (Visit 1) to Week 6 (Visit 3). The primary analysis for non-inferiority is conducted on the per-protocol analysis (PPA) population. An ANOVA model is used to adjust for dichotomous randomization strata: Week 0 FEV₁ % predicted, treatment combination at screening, prior study enrollment, and Week 0 age. The estimated effect of discontinuation and corresponding 95% confidence interval are reported, and the p-value is evaluated for a one-sided alpha-level 0.025 test of non-inferiority with a margin of -3% absolute change in FEV₁ % predicted. An unadjusted estimate is also provided.

The primary analysis is repeated in the ITT population. Missing outcome data in the ITT population were imputed using the least favorable treatment mean in arms discontinuing treatment and the most favorable treatment mean in arms continuing treatment. In this case, the least (most) favorable treatment mean is defined as the mean of the arm with the greater negative (positive) change from Week 0 to Week 6. Complete case results, including participants based on availability of non-missing values, are also reported.

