The following table summarizes the estimate for the difference in the change in CRISS score between intervention arms from Week 0 (Visit 1) to Week 6 (Visit 3) using an Analysis of Variance model. The models summarized are for an unadjusted model and one that adjusts for the randomization strata: Week 0 FEV₁ % Predicted (≥90% or <90%), therapy combination at screening (single or concurrent use of hypertonic saline and/or dornase alfa), prior study enrollment (yes or no), and Week 0 age (≥18 years or < 18 years).

Model Covariates	STOP Taking Mean Estimate	KEEP Taking Mean Estimate	Difference (95% CI)	P-value [9]
Per Protocol Analysis Population	(N=)	(N=)		
Model Unadjusted				
Intervention Arm:	STOP Taking hypertonic saline [1, 2]			
Model Adjusted for Randomization Strata				
Intervention Arm:	STOP Taking hypertonic saline [2, 3]			
Randomization Strata:	FEV ₁ % Predicted ≥90% [4] On both HS and Dnase [5] Prior study enrollment [6] Age ≥18 years [7]			
Intent to Treat Population [8]	(N=)	(N=)		
Model Unadjusted				
Intervention Arm:	STOP Taking hypertonic saline [1, 2]			
Model Adjusted for Randomization Strata				
Intervention Arm:	STOP Taking hypertonic saline [2, 3]			
Randomization Strata:	FEV ₁ % Predicted ≥90% [4] On both HS and Dnase [5] Prior study enrollment [6] Age ≥18 years [7]			

[1] The overall unadjusted intervention arm difference (STOP Taking - KEEP Taking) is estimated using a twosample t-test.

[2] Compared to reference level, KEEP taking hypertonic saline.

[3] Least Squares Mean Estimates from model with weighting proportional to observed frequencies of randomization factor combinations in the data.

[4] Compared to reference level, FEV₁ % Predicted < 90% at Week 0 (Visit 1).

[5] Compared to reference level, one therapy at Week -2 (Screening).

[6] Compared to reference level, no prior study enrollment.

[7] Compared to reference level, age <18 years at Week 0 (Visit 1).

[8] Missing values are imputed using the least favorable treatment mean in arms discontinuing treatment and using most favorable treatment mean in arms continuing treatment.
[9] Two-sided p-value.

Figure 9.2. Change in CFQ-R Respiratory Domain Scaled Score over Time (PPA and ITT population for Final Report)

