[6] Compared to reference level, no prior study enrollment.

[7] Compared to reference level, age <18 years at Week 0 (Visit 1).

[8] Missing values are imputed using the least favorable treatment mean in arms discontinuing treatment and using most favorable treatment mean in arms continuing treatment.

[9] Two-sided p-value.

Figure 9.4. Distribution of Impact of Changing Daily Therapies Scores (PPA and ITT population for Final Report)

This figure displays the distribution of participant responses to the Impact of Changing Daily Therapies questionnaire at Week 6 (Visit 3) for both intervention arms. The Impact of Changing Daily Therapies questionnaire asks a single question: "If you and your doctor agree in the future it is ok to stop one of these medications (hypertonic saline or dornase alfa), how would this impact your daily life?" The numbers at the top of the bars indicate the number of participants with the given response.

Table 9.7. Summary of Impact of Changing Daily Therapies Scores (PPA and ITT population for Final Report)

The following table summarizes, by intervention arm, Impact of Changing Daily Therapies score at Week 6 (Visit 3). The Impact of Changing Daily Therapies questionnaire asks a single question: "If you and your doctor agree in the future it is ok to stop one of these medications (hypertonic saline or dornase alfa), how would this impact your daily life?" Responses are mapped to numeric scores as follows: "Significantly positive impact" = 3, "Moderately positive impact" = 2, "Minimally positive impact" = 1, "No impact" = 0, "Minimally negative impact" = -1, "Moderately negative impact" = -2, "Significantly negative impact" = -3.

Visit	STOP Taking (N=)	KEEP Taking (N=)	Difference (95% CI); P-value [1]
Week 6 (Visit 3)			
	N (%)		
	Mean (SD)		
	Median		
	Min, Max		

[1] 95% confidence interval and p-value are calculated using a two-sample t-test. The difference is STOP Taking – KEEP Taking.

10 Summary of Anthropometric Measures

Figure 10.1. Change in Weight Percentile over Time for Participants Age < 18 years (PPA and ITT population for Final Report)

This figure displays the mean absolute change in weight percentile from Week 0 (Visit 1) to each post-randomization visit for both intervention arms. 95% pointwise confidence intervals (using t-distribution approximation) are included at each time point. The number of participants at each time point is included in a legend below the figure.

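### An imputation rule built for the one-sided non-inferiority analysis is reused for the two-sided ITT comparisons of CRISS, CFQ-R and LCI, where it treats benefit and harm of stopping unequally

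*SAP*

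**What the plan says.** **The rule.** SAP 2.4 covers the primary endpoint and three secondary instruments: "Missing outcome data in the ITT population for the final primary analysis and for key secondary analyses (CRISS, CFQ-R, and LCI) will be imputed". The values are "imputed using the least favorable treatment mean in arms discontinuing treatment and using the most favorable treatment mean in arms continuing treatment". SAP 3.2.6 explains the terms for FEV1 only: "the least (most) favorable treatment mean is defined as the mean of the arm with the greater negative (positive) change".

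**Its origin.** The SAP's table of changes records the extension: "Extended the missing data imputation method used for the primary endpoint for use in key secondary endpoints (CRISS, CFQ-R and LCI"). The reason given is consistency with the sensitivity analysis of the primary endpoint. The primary test, in Protocol 14.2, is a "one-sided alpha-level 0.025 test of non-inferiority with a margin of -3% absolute change".

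**Where it is applied.** Footnote 8 of Tables 9.2 (CRISS), 9.4 (CFQ-R respiratory), 9.6 (CFQ-R treatment burden) and 11.3 (LCI) attaches the rule to the ITT block: "Missing values are imputed using the least favorable treatment mean in arms discontinuing treatment and using most favorable treatment mean in arms continuing treatment". Footnote 9 of the same tables reads "Two-sided p-value".

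**What else is reported.** Each of the four tables also has a per-protocol (PPA) block, unadjusted and strata-adjusted, without this imputation. SAP 2.4 adds: "Complete case results, including participants based on availability of non-missing values, will also be reported". Table 6.2, for FEV1, has both a complete-case and an imputed ITT block. The four secondary tables have only the imputed one.

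**The concern.** In a non-inferiority setting, a rule that leans against stopping makes the claim harder to reach, and that is its purpose. A two-sided comparison asks a different question: is there a difference in either direction? A rule that pulls back one direction and leaves the other alone gives an estimate whose bias depends on the sign of the result, with a p-value that does not mean what two-sided implies.

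At stake are the strata-adjusted ITT estimates for the secondary patient-reported outcomes and LCI. Protocol 14.3 specifies strata-adjusted regression for these outcomes, and Protocol 14.1.1 names ITT as the population for secondary summaries. As the shells stand, the only estimate that is both adjusted and ITT is the imputed one.

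**Working it through.** **Inputs**
- Imputation rule and outcomes covered: SAP 2.4; footnotes 8 and 9 of Tables 9.2, 9.4, 9.6 and 11.3.
- Two-sided level 0.05: Protocol 14.1.
- About 200 randomized per arm: Protocol 6.1. This matters only for the power figures. LCI is measured in a subset.
- Missing fraction per arm, f: not given for these outcomes. Assumed 2%, 5%, 12% and 20%. The 12% borrows the loss allowance that SAP 1.2 uses to time the interim reviews. The 20% borrows the ceiling in Protocol 14.7 for attrition and non-adherence combined, so it probably overstates missing data.
- Further assumptions: the change score is what is imputed, values are missing completely at random, missingness is equal in both arms, and favorable is read clinically.

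**The plan's own figure.** The documents give no power or precision for CRISS, CFQ-R or LCI. The primary power reproduces: 154 per arm, SD 8.4, margin 3 and one-sided 0.025 give 88.0%, and 74.3% if the true difference is -0.5 (stated: 88% and 74%). Nothing below changes these.

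**Step 1: point estimate.** Let d be the observed mean change in STOP minus that in KEEP, scaled so that positive is better. Set the KEEP mean to 0 and the STOP mean to d.
- Harm (d < 0): the least favorable mean is STOP's own and the most favorable is KEEP's own. The completed difference is d.
- Benefit (d > 0): missing STOP values receive 0 and missing KEEP values receive d. The completed difference is (1 - mS)d - mK·d = d(1 - mS - mK), where mS and mK are the missing fractions in STOP and KEEP.

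Take a 4-point CFQ-R difference, the MCID shown in Figure 9.2:

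| Missing per arm | Benefit of 4 becomes | Harm of 4 becomes |
|---|---|---|
| 2% | 4 × 0.96 = 3.84 | 4.00 |
| 5% | 4 × 0.90 = 3.60 | 4.00 |
| 12% | 4 × 0.76 = 3.04 | 4.00 |
| 20% | 4 × 0.60 = 2.40 | 4.00 |

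**Step 2: standard error.** Filling a fraction f with a constant reduces the within-arm variance to about (1 - f)σ², while the sample size is counted as n instead of n(1 - f). The reported standard error is therefore about (1 - f) times the complete-case one.

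**Step 3: tails under no effect.** Write t for the complete-case statistic. On the harm side the imputed statistic is about t/(1 - f). On the benefit side it is about t(1 - 2f)/(1 - f). Hence
- harm tail = Φ(-1.96(1 - f))
- benefit tail = 1 - Φ(1.96(1 - f)/(1 - 2f))

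| Missing per arm | Harm tail | Benefit tail | Total |
|---|---|---|---|
| 2% | 2.7% | 2.3% | 5.0% |
| 5% | 3.1% | 1.9% | 5.1% |
| 12% | 4.2% | 1.2% | 5.4% |
| 20% | 5.8% | 0.4% | 6.3% |

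Repeated simulations of two-sample t-tests with 200 per arm agree with the tails to within about 0.2 percentage points (for example 4.1% to 4.3% and 1.1% to 1.3% at 12%).

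**Step 4: power for a true effect of 0.3 SD** (simulated, 200 per arm)

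| Missing per arm | Benefit, imputed | Harm, imputed | Complete case, either way |
|---|---|---|---|
| 2% | 83% | 85% | 84% |
| 5% | 80% | 85% | 83% |
| 12% | 70% | 86% | 80% |
| 20% | 51% | 87% | 76% |

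**Step 5: direction by outcome.** The SAP 3.2.6 definition is tied to FEV1, where a fall is unfavorable. CRISS scores 0 when a symptom is absent (Table 9.1), so a fall is an improvement. Applied literally to CRISS, that wording would reverse the asymmetry: harm would be shrunk and benefit would pass in full. The SAP does not say which reading a programmer should use, and it states no direction for LCI.

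**The case against.** Several points on the other side stand.

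- **Other estimates exist.** Each of the four tables has an adjusted PPA block without the imputation, and SAP 2.4 promises complete-case results. Tables 9.1, 9.3, 9.5 and 11.2 show observed-data ITT differences with confidence intervals and p-values, from a stratified randomization. A reader might infer that the trial as a whole will understate the benefit of stopping. The documents do not support that. They do leave a gap: the PPA drops non-adherent participants and those who start acute antibiotics, and the observed-data ITT differences are unadjusted.
- **Missing data may be low.** Protocol 11.1 asks early withdrawals to attend a final visit with Visit 3 procedures and keeps participants who change regimen in follow-up. SAP 2.4 allocates such data to the next scheduled visit. It would be wrong to read 12% as the SAP's expected missing rate for these outcomes.
- **Overall size stays near nominal.** The total two-sided error is 5.1% at 5% missing and 5.4% at 12%. What is distorted is the split between the tails, so calling the test invalid outright would go too far.
- **Treatment burden is not a listed protocol endpoint.** Protocol 5.2 names only the CFQ-R respiratory domain. A reader might single out Table 9.6 as the trial's main benefit measure, but it is a SAP analysis.
- **Leaning against stopping may be deliberate.** The trial is open label, dropout may depend on outcome, and an analysis assuming missing at random could flatter stopping. That is a good reason to keep the rule as a sensitivity analysis. It does not justify a two-sided p-value resting on it, since the rule also raises the false-harm rate.

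**Conclusion.** The concern holds for the two-sided ITT rows of Tables 9.2, 9.4, 9.6 and 11.3. The asymmetry in the point estimate is exact algebra once favorable is read clinically and change is imputed. Its size depends on a missing fraction that the documents do not give: a benefit loses 4% of its size at 2% missing per arm, 10% at 5% and 24% at 12%. Power for a 0.3 SD benefit is 1 point below complete case at 2%, about 3 points at 5% and about 10 at 12%. At 2% this is negligible; from 5% upward it is visible in the tails.

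A reader might infer that the primary non-inferiority conclusion is compromised. It is not: the primary analysis uses the PPA population, which requires a Week 6 FEV1, and the imputation enters only the ITT sensitivity analysis, where leaning against stopping is appropriate and a complete-case result stands beside it. Nor can it be said that every secondary outcome is biased against stopping, because direction is undefined outside FEV1 and the literal wording would reverse it for CRISS.

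**What to change.** 1. In Tables 9.2, 9.4, 9.6 and 11.3, add a strata-adjusted complete-case ITT row, laid out as in Table 6.2, and base the two-sided ITT p-value on it. Multiple imputation under missing at random is an acceptable alternative, using Week 0 values and, for CRISS and CFQ-R, Week 2 values (MBW is not scheduled at Week 2).
2. Keep the least/most favorable imputation as a labelled sensitivity row.
3. In SAP 2.4, state for each outcome which direction is favorable. For CRISS, a lower score is better.
4. Report the missing fraction by arm for each outcome, so that readers can judge how much the sensitivity row can move.

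The cost is a few sentences in the SAP and one further block in four table shells. No new data are needed, and the complete-case results are already promised in SAP 2.4.

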3.1. Screening Report

3.1.1. Outline of Screening and Enrollment

The overall flow from screening to enrollment is illustrated by a CONSORT diagram. The number of participants screened and eligible are summarized by site. The status of second study screening and enrollment among participants initially on both hypertonic saline and dornase alfa that completed their first study is summarized by first study and by intervention arm.

3.1.2. Screen Failures, Run-in Loss to Follow-up, and Reasons Not Randomized

Screen failure reasons are summarized for Week -2, the initial screening visit. Run-in periods initiated are tracked over time among study participants who are eligible at Week -2. Then, follow-up from Week -2 to Week 0 (Visit 1) is tabulated among participants eligible at initial screening. Participants not completing the Week 0 visit within the allowed window (21 days after the Week -2 visit) are categorized as an incomplete run-in. Finally, reasons for ineligibility at randomization or decision to not randomize are given. Ineligibility reasons are summarized for Week 0 (Visit 1) and by current therapy and prior enrollment status.

3.1.3. Enrollment, Demographics, and Follow-up Overview

Total participants randomized in each study and their eligibility before randomization (Study A, Study B, or both) is summarized overall and broken down by therapy regimen/prior enrollment. Demographic and Week 0 characteristics for unique participants enrolled are summarized among all randomized participants by study. All measures were recorded at Visit 1 unless specified otherwise.

3.2. Study Reports

3.2.1. Summary of Randomization and Study Visit Completion

A CONSORT diagram for the corresponding study (A or B) delineates counts of participants from randomization to per-protocol analysis population inclusion. The cumulative monthly enrollment of

participants randomized into the study is graphically summarized. Participants randomized, withdrawn, and completing the study are tabulated by intervention arm and site.

Completion of each study visit and clinic spirometry at each visit are summarized by intervention arm and overall. Participants are considered to have completed the visit if there is a CRF page with a study date corresponding to that visit.

An overview of analysis populations summarizes the number of participants, by intervention arm and in total, excluded from the per-protocol analysis population for one or more reasons. The reasons for exclusion are also summarized.

3.2.2. Demographics and Characteristics at Week 0

Intervention arms are described and compared with respect to Week 0 demographic and clinical characteristics including age, sex, CFTR genotype, race, height, weight, and all randomization strata. For all summarizations, Week 0 clinical characteristics are defined as measurements obtained at Visit 1 unless specified otherwise.

